Nudging High Emergency Department Utilizers to Consider Non-emergent Healthcare
Resources
(NCT)

Study Protocol with Statistical Analysis Plan

January 29, 2025

Study Protocol

Background

The goal of this campaign is to reduce unnecessary emergency department (ED) visits/encourage patients who have visited a Geisinger Emergency Department four (4) or more times within the last 6 months to seek care through alternatives to ED use when appropriate. In this campaign, patients will receive outreach aligned with this goal following ED discharge and will be assigned to outreach via an interactive chatbot message or a live phone call from a Community Health Worker (CHW) or Certified Medical Assistant (CMA).

The study will assess whether ED use differs across patients in different outreach conditions.

Design

This study is a randomized controlled trial with two study arms. Patients will be randomized to receive (1) a call from a CHW or CMA or (2) a message from an interactive Artera chatbot upon ED discharge.

Methods

At the time of an eligible patient's discharge from the ED, that patient will be assigned to one of the following study arms, based on which of several ranges of randomized numbers that patient was originally assigned in their electronic chart:

1. Current standard practice (control arm): Patients in this arm will receive the current standard system outreach (i.e., call from CHW or CMA).
2. Interactive chatbot outreach (treatment arm): Patients in this arm will receive outreach from an interactive chatbot.

Power Analysis

The power calculation has been modified from the original estimation, given less-than-expected eligible patients over time. With 2,279 patients, we would have 80% power to detect a 5.0% absolute decrease in ED visits between the active arm and the control arm, with two-tailed alpha of .15, assuming a 50% baseline rate of subsequent ED visits within 120 days. The target effect size and number of patients are largely informed by practical considerations regarding the acceptable duration of the intervention (maximum of 7 months, regardless of whether the full sample is achieved), with an effect deemed useful if achieved.

Project Status

The intervention has not yet begun.

Statistical Analysis Plan

Planned Analyses

Primary Outcome: ED use [Time Frame: within 120 days following day of discharge]

Question: Does outreach decrease ED visits when including an automated text chatbot instead of live outreach?

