Analysis (Confirmatory): We will test the hypothesis that outreach from an interactive chatbot versus a CHW or CMA decreases the likelihood patients will visit the ED in the 120 days following day of discharge. We will run an OLS regression including a categorical predictor variable coding for experimental arm (0 = control arm, 1 = treatment arm).

Other Pre-specified Outcomes

We will run the analysis described above on the following additional outcomes:

1. Contact with patient by monitoring center, CMA, or CHW

Contact with patient by monitoring center, CMA, or CHW (yes/no)

[Time Frame: within 3 business days following day of discharge]

2. Contact with patient by monitoring center, CMA, or CHW

Contact with patient by monitoring center, CMA, or CHW (yes/no)

[Time Frame: within 5 business days following day of discharge]

3. Time to successful contact by monitoring center, CMA, or CHW

Number of business days to successful contact by monitoring center, CMA, or CHW

4. Interaction of patient with Artera chatbot

Interaction of patient with Artera chatbot (yes/no)

[Time Frame: within 7 calendar days following first Artera outreach]

5. ED use

ED use (yes/no)

[Time Frame: within 30 days following day of discharge]

6. ED use

ED use (yes/no)

[Time Frame: within 30 days following day of outreach by Artera or CMA/CHW]

Analysis Notes

Recent work suggests that OLS regressions are appropriate in randomized experiments with binary outcome variables such as ours (Gomila, 2021).

Reference

Gomila, R. (2021). Logistic or linear? Estimating causal effects of experimental treatments on binary outcomes using regression analysis. *Journal of Experimental Psychology: General*, 150(4), 700-709. <https://doi.org/10.1037/xge0000920>

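### Item 6 starts its 30-day ED window at outreach, which happens after assignment, so its arm comparison is not protected by randomization

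*Combined protocol and SAP*

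**What the plan says.** The Methods section of the protocol fixes the arm at discharge: "At the time of an eligible patient's discharge from the ED, that patient will be assigned to one of the following study arms". The Design section describes the two interventions as "a call from a CHW or CMA or (2) a message from an interactive Artera chatbot upon ED discharge". No calendar day for outreach is fixed in either arm.

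Three ED-use outcomes are planned, with these time origins:

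- Primary: "Primary Outcome: ED use [Time Frame: within 120 days following day of discharge"
- Item 5: "Time Frame: within 30 days following day of discharge"
- Item 6: "Time Frame: within 30 days following day of outreach by Artera or CMA/CHW"

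The lead-in to the additional outcomes reads "We will run the analysis described above on the following additional outcomes". Item 6 therefore gets the same OLS regression on the arm indicator as the primary outcome.

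Item 4 is specific about which outreach starts its clock: "Time Frame: within 7 calendar days following first Artera outreach". Item 6 does not say whether it means a first attempt, a later attempt or a completed call. No rule covers patients with no outreach date, or ED visits that fall between discharge and outreach.

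**The concern.** Randomization balances the arms at discharge. It does not balance when outreach happens or who ends up with an outreach date, because both come after assignment and can depend on the channel being tested. The different channel is the treatment and is no flaw in itself. The problem is that the delivery of that treatment also starts the outcome clock.

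Three things can then differ between arms with no treatment effect at all:

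1. **Position of the window.** If ED return risk is highest soon after discharge, the arm reached earlier is observed over a higher-risk stretch and looks worse.
2. **Visits left out.** Returns between discharge and outreach do not count, and a longer lag leaves out more of them.
3. **Membership.** A patient without an outreach date has no window. If such patients are dropped, and they are more common in one arm or differ in risk, the patients compared are no longer those randomized.

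A reader would take a pre-specified arm difference on item 6 as a randomized result. The plan has no rule for separating a treatment effect from these artefacts.

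**Working it through.** The plan gives no figure for item 6 that could be reproduced, so the check has two parts: the order of events, and an illustration of how large the artefact could be.

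**Order of events.** Assignment is at discharge (Methods) and outreach comes after it (Background). The primary outcome and item 5 start at discharge, an origin common to both arms. Item 6 starts at outreach. It is the only ED-use outcome whose origin is a post-assignment event.

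**Inputs for the illustration**

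- From the Power Analysis: 50% with an ED visit within 120 days; N = 2,279; two-tailed alpha .15. That alpha is stated for the primary outcome. No level is given for item 6, so .05 is shown as well.
- Assumed: no treatment effect; equal arms of 2,279/2 = 1,139.5; Weibull cumulative hazard with shape k; outreach on one fixed day d in each arm.

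**Formulas**

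- Cumulative hazard: H(t) = ln2 × (t/120)^k, which gives 50% at day 120.
- Risk in the window: P(d) = 1 − exp(−[H(d+30) − H(d)]).
- Rejection rate under no effect: Φ(diff/SE − z) + Φ(−diff/SE − z), with z = 1.440 at .15 and 1.960 at .05, and SE unpooled.

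**One case in full (k = 0.7, day 1 against day 4)**

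- H(31) − H(1) = 0.2688 − 0.0243 = 0.2445, so P(1) = .2169.
- H(34) − H(4) = 0.2867 − 0.0641 = 0.2226, so P(4) = .1996.
- Difference = 1.7 points and SE = 1.70 points, so diff/SE = 1.02.
- Rejection rate = 34% at .15 and 17% at .05.

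**Day 1 against day 4 (three-day gap)**

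| Shape k | P(1) | P(4) | Difference (points) | Rejection at .15 | Rejection at .05 |
|---|---|---|---|---|---|
| 1.0 | .1591 | .1591 | 0 | 15% | 5% |
| 0.9 | .1777 | .1733 | 0.4 | 17% | 6% |
| 0.8 | .1972 | .1871 | 1.0 | 23% | 9% |
| 0.7 | .2169 | .1996 | 1.7 | 34% | 17% |
| 0.6 | .2355 | .2096 | 2.6 | 52% | 32% |

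**Day 1 against day 2 (one-day gap)**

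| Shape k | Difference (points) | Rejection at .15 | Rejection at .05 |
|---|---|---|---|
| 0.8 | 0.4 | 16% | 6% |
| 0.7 | 0.7 | 19% | 7% |
| 0.6 | 1.1 | 23% | 10% |

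A three-day gap that starts earlier (day 0.5 against 3.5) gives 1.2 / 2.0 / 3.1 points for shapes 0.8 / 0.7 / 0.6. Starting one arm at day 0 gives larger figures, but a Weibull hazard with shape below 1 is infinite at time zero, so I give those no weight.

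For scale, at 20% risk the SE of the arm difference is √(2 × .2 × .8 / 1,139.5) = .0168, or 1.7 points.

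**Membership.** Suppose 10% of one arm has no outreach date and is left out, with 30% risk against an arm average of 20%. The remaining rate is (.20 − .10 × .30)/.90 = .189, a shift of −1.1 points. If the omitted patients had average risk, the shift would be 0. This example is also hypothetical.

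**The case against.** The best defence is that the plan already holds the protected comparison. Item 5 is the same endpoint over 30 days from discharge, and item 6 can be read as its companion. Only the 120-day primary is labelled confirmatory, and no decision in the plan depends on item 6. This stands, and it limits the weight of the point.

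A second argument is that the Design section places outreach upon ED discharge, which can be read as covering both arms, and that Methods says patients in both arms will receive it. If outreach means a first attempt made promptly for everyone, lag differences and missing dates would be small. The business-day windows in items 1 and 2 and the business-day count in item 3 concern contact, not attempts, so they do not show that attempts lag. This is fair: the documents contain no evidence that timing differs between arms. They do not establish equal timing either. If every outreach fell on the day of discharge, item 6 would duplicate item 5, so listing both suggests that the dates were expected to differ.

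Third, the lags, hazard shapes and non-outreach rate above are all assumed, and with a one-day gap the inflation is modest (16% to 23% against a nominal 15%). That also stands. The figures show what the rule permits, not what will happen.

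**Conclusion.** The point holds. As written, item 6 compares arms over windows whose start and membership depend on an event after assignment, and the plan tests that comparison as if randomization protected it.

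The size and direction of any bias cannot be determined from the documents. It would be nil with a constant hazard and a complete set of outreach dates, or with equal lags and complete dates. Under the assumed front-loaded hazards (shapes 0.8 to 0.6), a one-day gap produces about 0.4 to 1.1 points and a three-day gap from day 1 about 1.0 to 2.6 points, against a standard error of roughly 1.7. Dropping undated patients could add to this or offset it.

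Only this one non-primary outcome is affected. The primary outcome and item 5 are not, and nothing here puts the trial's main conclusion at risk. It should be corrected because the correction is cheap and the protocol states that the intervention has not started.

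**What to change.** Name item 5, in all randomized patients, as the 30-day arm comparison. Then do one of the following for item 6:

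- **(a) Report it descriptively by arm**, labelled as a non-randomized comparison. Define the day of outreach in the same way for both arms (for example, first attempt). Show by arm the outreach lag, the ED visits between discharge and outreach, and the number of patients with no outreach date.
- **(b) Re-anchor it** to one common start day counted from discharge and applied to every randomized patient in both arms. This keeps a randomized test, but the result will be close to item 5.

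I would choose (a), since item 5 already supplies the randomized 30-day test and (a) keeps the operational information.

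The cost is SAP wording. The arm test of the outreach-anchored window is given up, and randomization did not protect that test.
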